### **13.4 Quality Control and Quality Assurance**

Novartis maintains a robust Quality Management System (QMS) that includes all activities involved in quality assurance and quality control, to ensure compliance with written Standard Operating Procedures as well as applicable global/local GCP regulations and ICH Guidelines.

Audits of investigator sites, vendors, and Novartis systems are performed by auditors, independent from those involved in conducting, monitoring or performing quality control of the clinical trial. The clinical audit process uses a knowledge/risk based approach.

Audits are conducted to assess GCP compliance with global and local regulatory requirements, protocols and internal SOPs, and are performed according to written Novartis processes.

### **13.5 Participant Engagement**

The following participant engagement initiatives are included in this study and will be provided, as available, for distribution to study participants at the timepoints indicated. If compliance is impacted by cultural norms or local laws and regulations, sites may discuss modifications to these requirements with Novartis.

- Thank You letter
- Plain language trial summary - after CSR publication
- Individual study results - after CSR publication
- Trial Feedback Questionnaires (TFQ) - start and end of trial

### **13.6 Data Protection**

Participants will be assigned a unique identifier by Novartis. Any participant records or datasets that are transferred to Novartis will contain the identifier only; participant names or any information which would make the participant identifiable will not be transferred.

The participant must be informed that his/her personal study-related data will be used by Novartis in accordance with local data protection law. The level of disclosure must also be explained to the participant who will be required to give consent for their data to be used as described in the informed consent.

The participant must be informed that his/her medical records may be examined by Clinical Quality Assurance auditors or other authorized personnel appointed by Novartis, by appropriate IRB/IEC members, and by inspectors from regulatory authorities.

Novartis has appropriate processes and policies in place to handle personal data breaches according to applicable privacy laws.

## **14 Protocol adherence**

This protocol defines the study objectives, the study procedures and the data to be collected on study participants. Additional assessments required to ensure safety of participants should be administered as deemed necessary on a case by case basis. Under no circumstances including incidental collection is an investigator allowed to collect additional data or conduct any additional procedures for any purpose involving any investigational drugs under the protocol, other than the purpose of the study. If despite this interdiction prohibition, data, information, observation would be incidentally collected, the investigator shall immediately disclose it to Novartis and not use it for any purpose other than the study, except for the appropriate monitoring on study participants.

Investigators ascertain they will apply due diligence to avoid protocol deviations. If an investigator feels a protocol deviation would improve the conduct of the study this must be considered a protocol amendment, and unless such an amendment is agreed upon by Novartis and approved by the IRB/IEC and Health Authorities, where required, it cannot be implemented.

## **14.1 Protocol amendments**

Any change or addition to the protocol can only be made in a written protocol amendment that must be approved by Novartis, health authorities where required, and the IRB/IEC prior to implementation.

Only amendments that are required for participant safety may be implemented immediately provided the health authorities are subsequently notified by protocol amendment and the reviewing IRB/IEC is notified.

Notwithstanding the need for approval of formal protocol amendments, the investigator is expected to take any immediate action required for the safety of any participant included in this study, even if this action represents a deviation from the protocol. In such cases, Novartis should be notified of this action and the IRB/IEC at the study site should be informed according to local regulations.

## 16 Appendices

### 16.1 Appendix 1: Clinically notable laboratory values and vital signs

The central laboratory will flag laboratory values falling outside of the normal ranges on the central laboratory reports. Investigators are responsible for reviewing these abnormal values for clinical significance, signing the laboratory reports to indicate their review, and reporting values considered clinically significant in the appropriate eCRF.

Any clinically significant abnormal laboratory value should be evaluated and followed-up by the investigator until normal or a cause for the abnormality is determined.

See [Section 16.2](#) for specific liver event and laboratory test trigger definitions and follow-up requirements.

## 16.2 Appendix 2: Liver event and laboratory trigger definitions & follow-up requirements

**Table 16-1 Liver laboratory trigger definitions**

Liver laboratory triggers	Definition/ threshold
If ALT, AST and TBL normal at baseline:	
 
• ALT or AST > 3.0 x ULN
 
• TBL > 1.5 x ULN
 
• ALP > 2.0 x ULN (in the absence of known bone pathology)
 

If ALT, AST, or TBL abnormal at baseline:	
 
• ALT or AST > 2 x baseline or > 300 U/L, whichever occurs first
 
• TBL > 2 x baseline and > 2.0 x ULN
 

**Table 16-2 Follow-up requirements for liver laboratory triggers - ALT, AST, TBL**

ALT or AST	TBL	Liver Symptoms	Action
ALT or AST increase without TBL increase:			
If normal at baseline: ALT or AST > 3.0 x ULN	Normal For participants with Gilbert's syndrome: No change in baseline TBL	None	
 
• No change to study treatment
 
• Measure ALT, AST, ALP, GGT, TBL, PT/INR, albumin, CK, and GLDH in 48-72 hours.
 
• Follow-up for symptoms.
 

If elevated at baseline: ALT or AST > 2 x baseline			
If normal at baseline: ALT or AST > 5.0 x ULN for more than two weeks	Normal For participants with Gilbert's syndrome: No change in baseline TBL	None	
 
• Interrupt study treatment
 
• Measure ALT, AST, ALP, GGT, TBL, PT/INR, albumin, CK, and GLDH in 48-72 hours.
 
• Follow-up for symptoms.
 
• Initiate close monitoring and workup for competing etiologies.
 

If elevated at baseline: ALT or AST > 3 x baseline for more than two weeks			
If normal at baseline: ALT or AST > 8.0 x ULN	Normal	None	
 
• Study treatment can be restarted only if another etiology is identified and liver enzymes return to baseline.
 
• If no cause can be identified to explain the elevation in liver enzymes, then study treatment must be discontinued.
 

ALT or AST increase with TBL increase:			
If normal at baseline: ALT or AST > 3.0 x ULN	TBL > 2.0 x ULN (or INR > 1.5) For participants with Gilbert's syndrome: Doubling of direct bilirubin	None	
If elevated at baseline: ALT or AST > 2 x baseline			
If normal at baseline: ALT or AST > 3.0 x ULN	Normal or elevated	Severe fatigue, nausea, vomiting, right upper quadrant pain	
If elevated at baseline: ALT or AST > 2 x baseline			

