### **6.6.2 Dose modifications**

There are no dose adjustments or modifications of study treatment [i.e., study drug (s.c. inclisiran/placebo) or control drug (p.o. ezetimibe/placebo)]. For study treatment interruptions, discontinuations, and other follow-up requirements, please refer to [Section 10.1.1](#), [Section 10.2.1](#), [Table 16-2](#), and [Table 16-3](#).

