## 9 Discontinuation and completion

### 9.1 Discontinuation from study treatment and from study

#### 9.1.1 Discontinuation from study treatment

Discontinuation of study treatment for a participant occurs when study treatment is permanently stopped for any reason (prior to the planned completion of study drug or control drug administration, if any) and can be initiated by either the participant or the investigator. If the participant permanently discontinues p.o. ezetimibe/placebo or s.c. inclisiran/placebo, then the participant's entire study treatment must be stopped. The treatment disposition CRF will be completed to reflect that the participant has permanently discontinued study treatment (both p.o. study drug and s.c. study drug).

The investigator must discontinue study treatment for a given participant if he/she believes that continuation would negatively impact the participant's well-being.

Discontinuation from study treatment is required under the following circumstances:

- Participant/guardian decision
- Pregnancy
- Use of prohibited treatment as per recommendations in the prohibited medication [Section 6.2.2](#)
- Any situation in which continued study participation might result in a safety risk to the participant
- Severe and persistent (> 14 days despite appropriate treatment) reactions at the injection site and any type of anaphylactic reactions
- Intolerable adverse events
- Unexplained increases in transaminases (ALT or AST) or total bilirubin confirmed by repeat test as follows:
  - ALT or AST > 8 x ULN
  - ALT or AST > 5 x ULN for more than 2 weeks
  - ALT or AST > 3 x ULN with simultaneous or subsequent elevation of total bilirubin > 2 x ULN
  - ALT or AST > 3 x ULN with the appearance of fatigue, nausea, vomiting, right upper quadrant pain or tenderness, fever, rash, and/or eosinophilia (> 5%)

The investigator should evaluate to see if other causes for the laboratory abnormalities are immediately apparent, such as obstructive gall bladder or bile duct disease, viral or alcoholic hepatitis, malignancy involving the liver, congestive hepatopathy, other hepatotoxins or heritable disorders. Please also refer to [Section 16.2 Appendix 2](#).

- Unexplained CK > 10 x ULN confirmed by repeat test when the CK elevation is associated with muscle pain, muscle tenderness and/or muscle weakness, or new onset renal dysfunction with no other alternative explanation
- Following emergency unblinding

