## **10.2 Additional Safety Monitoring**

### **10.2.1 Liver safety monitoring**

To ensure participant safety and enhance reliability in determining the hepatotoxic potential of an investigational drug, a standardized process for identification, monitoring and evaluation of liver events has to be followed.

Please refer to [Table 16-1](#) in [Section 16.2](#) for complete definitions of liver laboratory triggers.

Once a participant is exposed to study treatment, every liver event defined in [Table 16-1](#) should be followed up by the investigator or designated personnel at the trial site, as summarized below. Additional details on actions required in case of liver events are outlined in [Table 16-2](#) and [Table 16-3 \(Section 16.2\)](#). Repeat liver chemistry tests (i.e., ALT, AST, TBL, albumin, CK, GLDH, PT/INR, ALP and GGT) to confirm elevation. These liver chemistry repeats will be performed using the central laboratory. If results will not be available from the central laboratory, then the repeats can also be performed at a local laboratory to monitor the safety of the participant. If a liver event is subsequently reported, any local liver chemistry tests previously conducted that are associated with this event should have results recorded on the appropriate eCRF.

- If the initial elevation is confirmed, close observation of the participant will be initiated, including consideration of treatment interruption if deemed appropriate.
- Discontinuation of the investigational drug (refer to the Discontinuation of study treatment section), if appropriate
- Hospitalization of the participant if appropriate
- Causality assessment of the liver event
- Thorough follow-up of the liver event should include (based on investigator's discretion): serology tests, imaging and pathology assessments, hepatologist's consultancy; obtaining more detailed history of symptoms and prior or concurrent diseases, history of concomitant drug use, exclusion of underlying liver disease

All follow-up information and procedures performed must be recorded as appropriate in the eCRF.

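### For some participants with raised baseline ALT/AST, Table 16-2 leaves dosing unchanged where Section 9.1.1 requires it to stop

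*Protocol*

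**What the plan says.** Protocol Section 9.1.1 is worded as a mandate: "Discontinuation from study treatment is required under the following circumstances". Its transaminase entries include "ALT or AST > 8 x ULN" and "ALT or AST > 5 x ULN for more than 2 weeks". They apply to unexplained rises confirmed by a repeat test and make no distinction by baseline value.

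Table 16-2 (Section 16.2, Appendix 2) does distinguish by baseline. With normal total bilirubin and no liver symptoms, a participant whose ALT/AST was raised at baseline meets the first row at more than twice baseline. The action there is "No change to study treatment", with repeat tests at 48 to 72 hours and symptom follow-up. The row has no upper limit. Interruption for raised baselines needs "ALT or AST > 3 x baseline for more than two weeks". The row for "ALT or AST > 8.0 x ULN" is labelled for normal baselines and has no raised-baseline counterpart.

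On routing, Section 6.6.2 reads "For study treatment interruptions, discontinuations, and other follow-up requirements, please refer to" and then lists Sections 10.1.1 and 10.2.1 and Tables 16-2 and 16-3, but not Section 9.1.1. Section 10.2.1 does point onward, in softer terms: "Discontinuation of the investigational drug (refer to the Discontinuation of study treatment section), if appropriate". Section 9.1.1 adds a reference to Appendix 2. Nothing says which text prevails.

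**The concern.** Raised baselines can enter the trial, because exclusion criterion 9 removes unexplained ALT/AST only above 3 x ULN at screening. For these participants a fixed multiple of ULN and a multiple of their own baseline are different thresholds, so the two instructions can disagree.

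What is at stake is participant safety. In Table 8-1, Day 30 is the only scheduled post-dose chemistry before Day 150. A site acting on the no-change row after a Day 30 rise could continue daily capsules, and in some cases give the Day 90 injection, where Section 9.1.1 requires both to stop.

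A second mismatch applies at any baseline. The Section 9.1.1 symptom criterion counts fatigue of any degree, fever, rash and eosinophilia. The symptom row of Table 16-2 counts fatigue only when severe and omits the other three.

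**Working it through.** The plan gives no figure to reproduce; this is a comparison of thresholds.

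**Notation.** *b* is baseline ALT or AST and *v* the on-treatment value, both in multiples of ULN. Bilirubin is normal, there are no symptoms, and the rise is unexplained and confirmed. Raised baseline means 1 < *b* ≤ 3, the upper end taken from exclusion criterion 9.

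**Rules.**
- Section 9.1.1: stop if *v* > 8, or if *v* > 5 for more than two weeks.
- Table 16-2, raised baseline: interrupt if *v* > 3*b* for more than two weeks; otherwise no change if *v* > 2*b*. The 8 x ULN row does not apply.

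**Normal baseline, as a check.** The table's interruption limits are 8 x ULN, and 5 x ULN for more than two weeks, the same as Section 9.1.1. There is no conflict.

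**Case (a): above 5 x ULN for more than two weeks.** The rules conflict when max(5, 2*b*) < *v* ≤ 3*b*. This needs 3*b* > 5, so *b* > 5/3 = 1.67. If 2*b* > 5, so *b* > 2.5, values from 5 up to 2*b* match no row of the table.

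| *b* | 2*b* | 3*b* | Table: no change; 9.1.1: stop | No table row; 9.1.1: stop |
|---|---|---|---|---|
| 1.5 | 3.0 | 4.5 | none | none |
| 2.0 | 4.0 | 6.0 | above 5, up to 6 | none |
| 2.5 | 5.0 | 7.5 | above 5, up to 7.5 | none |
| 3.0 | 6.0 | 9.0 | above 6, up to 9 | above 5, up to 6 |

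Worked example: *b* = 2.5 and *v* = 6 for three weeks. The ratio to baseline is 6 / 2.5 = 2.4, which is above 2 and below 3. Table 16-2 gives no change; Section 9.1.1 gives discontinuation.

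**Case (b): above 8 x ULN, first two weeks.** The raised-baseline interruption row cannot yet apply. Since 2*b* ≤ 6 < 8, every such value falls in the no-change row, for every raised *b* up to 3. If the 48 to 72 hour retest confirms the rise and it is judged unexplained at once, the conflict lasts 14 − 3 = 11 to 14 − 2 = 12 days.

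**Case (b): above 8 x ULN, beyond two weeks.** The conflict remains only for 8 < *v* ≤ 3*b*, which needs *b* > 8/3 = 2.67. At *b* = 3 the band is above 8, up to 9, and lies inside the case (a) band.

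Stepping *v* by 0.01 x ULN over selected baselines from 0.8 to 3 gave the same bands.

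**The case against.** The strongest reply is that the two texts are sequential. The no-change row is an initial response with a retest, and Section 9.1.1 applies only after confirmation. Section 6.6.2 names Section 10.2.1, which leads on to the discontinuation section, and Section 9.1.1 also has general safety and investigator-judgement clauses. This reading is fair at first detection. It does not cover case (a), where the rise has by definition lasted more than two weeks, and the row gives no action for a confirmed rise. The route through Section 10.2.1 turns a requirement into something done if judged appropriate.

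A second reply limits the harm, and much of it stands. If a rise above 8 x ULN at Day 30 persists, then for *b* up to 2.67 it exceeds three times baseline and the interruption row applies after two weeks, well before Day 90. The exposure at stake is then about 11 to 12 days of capsules, which are placebo in the inclisiran arm. The Day 90 injection is at risk only in sustained case (a), with a baseline above 2.67 x ULN, or when a confirmed rise falls back within two weeks. A work-up of other causes could also shorten the 11 to 12 days.

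Third, the 3 x ULN limit applies at screening, while baseline is the last value before first dose and chemistry is drawn again on Day 1. A baseline above 3 is therefore possible. The conflict remains: at *b* = 3.5 the sustained band runs from 7 to 10.5 x ULN, and values above 8 still exceed 2*b* = 7.

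Finally, baseline-relative limits could be deliberate. However, Table 16-1 adds an absolute 300 U/L limit for abnormal baselines, and SAP Table 2-2 defines elevation for raised baselines with an 8 x ULN alternative. Amendment 1 says Table 16-2 was revised to agree with Section 9.1.1, which I take only as evidence of intent.

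**Conclusion.** The concern holds. For raised baseline ALT/AST with normal bilirubin and no symptoms, Table 16-2 leaves treatment unchanged where Section 9.1.1 requires discontinuation. The sustained conflict needs a baseline above 1.67 x ULN. The conflict above 8 x ULN covers every raised baseline up to 3 x ULN in the first two weeks, and continues after that only for baselines above 2.67 x ULN. The raised-baseline interruption row is itself compatible with Section 9.1.1, since it ends in discontinuation when no cause is found.

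The documents give no rate of raised baselines. I assume few of about 300 participants would be affected, with negligible effect on either primary estimand. The bands take 3 x ULN as the highest baseline and depend only on the row labels and the no-change action. This should be fixed on safety grounds.

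**What to change.** - State in Table 16-2 and Section 6.6.2 that the Section 9.1.1 discontinuation criteria apply at any baseline and override the no-change row.
- Extend the 8 x ULN row to raised baselines.
- Set the raised-baseline interruption limit, for more than two weeks, at the lower of 3 x baseline and 5 x ULN. This also closes the band that matches no row.
- Use the Section 9.1.1 symptom list in Table 16-2.

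The cost is wording in one table and one cross-reference, with no new assessments. A few more participants with raised baselines may be interrupted or discontinued, as Section 9.1.1 already requires when the rise is confirmed and unexplained.

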**Table 16-3 Follow-up requirements for liver laboratory triggers - Isolated Hyperbilirubinemia or elevated ALP**

Criteria	Actions required	Follow-up monitoring
Elevated TBL (isolated)		
> 1.5 – 3.0 x ULN	
 
Maintain treatment
 
Repeat LFTs within 48-72 hours
 
	Monitor LFTs weekly until resolution to $\leq$ Grade 1 ( $\leq 1.5 \times$ ULN) or to baseline
> 3.0 - 10.0 x ULN (in the absence of known Gilbert syndrome)	
 
Interrupt treatment
 
Repeat LFT within 48-72 hours
 
Hospitalize if clinically appropriate
 
Establish causality
 
Record the AE and contributing factors (e.g. concomitant medications, medical history, lab) in the appropriate eCRF
 
	Monitor LFTs weekly until resolution to $\leq$ Grade 1 ( $\leq 1.5 \times$ ULN) or to baseline (ALT, AST, TBL, albumin, CK, GLDH, PT/INR, ALP and GGT) Test for hemolysis (e.g. reticulocytes, haptoglobin, unconjugated [indirect] bilirubin)
> 10.0 x ULN	
 
Discontinue the study treatment immediately
 
Hospitalize the participant
 
Establish causality
 
Record the AE and contributing factors (e.g. concomitant medications, medical history, lab) in the appropriate eCRF
 
	ALT, AST, TBL, albumin, CK, GLDH, PT/INR, ALP and GGT until resolution (frequency at investigator discretion)
Any AE potentially indicative of a liver toxicity	
 
Consider study treatment interruption or discontinuation
 
Hospitalization if clinically appropriate
 
Establish causality
 
Record the AE and contributing factors (e.g., concomitant medications, medical history, lab) in the appropriate eCRF
 
	Investigator discretion
Elevated ALP (isolated)		
> 2.0 x ULN	
 
Maintain treatment
 
Repeat LFTs within 48-72 hours
 
	Investigator discretion Monitor LFT within 1 to 4 weeks or at next visit

Based on investigator's discretion investigation(s) for contributing factors for the liver event can include: Serology tests, imaging and pathology assessments, hepatologist's consultancy; obtaining more detailed history of symptoms and prior or concurrent diseases, history of concomitant drug use, exclusion of underlying liver disease.

---

**16.3 Appendix 3: Specific Renal Alert Criteria and Actions and Event Follow-up**

Refer to [Section 10.2.2](#).

Clinical Development

KJX839/inclisiran/Leqvio®

CKJX839D12304 / NCT05763875

A Double-blind, Randomized, Placebo- and Active-Comparator Controlled Study to Evaluate the Efficacy of Inclisiran as Monotherapy in Patients with Primary Hypercholesterolemia Not Receiving Lipid-Lowering Therapy (VictORION-Mono)

Statistical Analysis Plan (SAP)

Document type: SAP Documentation

Document status: Final Amendment 1

Release date: 21-Jun-2024

Number of pages: 34

Property of Novartis
Confidential

May not be used, divulged, published or otherwise disclosed
without the consent of Novartis

Document History – Changes compared to previous final version of SAP

Date	Time point	Reason for update	Outcome for update	Section and title impacted (Current)
23-Mar-2023	Prior to DB lock	Creation of final DB version	N/A - First version	NA
21-Jun-2024	Prior to DB lock	Creation of amendment 1	Clarified the details about how the treatment group in SAF will be determined based on the study treatment actually received.	Section 2.2 Analysis sets
			Updated the subgroup definitions and the scope of subgroup analyses.	Section 2.2.1 Subgroup of interest
			Clarified that for subjects who discontinued study treatment prematurely, the compliance will only be summarized up to last p.o. treatment date + 1 day. Added details about handling of missing compliance data in cumulative compliance calculation.	Section 2.4.1 Study treatment / compliance
			Specified that the exposure to p.o. and s.c. study treatment will be summarized separately.	Section 2.4.1 Study treatment / compliance
			Updated the missing value imputation method for Treatment-policy Estimand.	Section 2.5.3 Handling of intercurrent events
			Added the details about tipping point analyses.	Section 2.5.5 Sensitivity analyses
			Instead of using models with interaction terms with subgroup variables, subgroup analyses will be	Section 2.5.6 Supplementary analyses

Date	Time point	Reason for update	Outcome for update	Section and title impacted (Current)
			performed by running the primary analysis model within each subgroup.	
			Sensitivity analysis will be conducted for the primary endpoint only.	Section 2.6 Analysis supporting secondary objectives
			eGFR will be summarized by categories: Severe, Moderate, Normal or Mild.	Section 2.7.3 Laboratory data
			Added summary of COVID-related AEs	Section 2.8 Impact of COVID-19
